IRB PROTOCOL

Sponsor / Study Title: **The Effectiveness of DSLT in Asian Normal Tension Glaucoma Patients**

Protocol # **NTG_DSLT-001**

Investigator/ Sponsor **[name] and [name]**

[contact]**

Address: **[name]
[name]**

CONFIDENTIAL

This protocol contains confidential information. Further dissemination, distribution, or copying of this protocol or its contents is strictly prohibited.

Background:

Normal-tension glaucoma (NTG) is a form of open-angle glaucoma characterized by glaucomatous optic neuropathy in patients with intraocular pressure (IOP) measurements consistently lower than 21 mmHg¹ and has been shown to account for the majority of primary open-angle glaucoma (POAG) in the

population older than 40 years in Asian countries.² Lowering IOP remains the only proven intervention to delay progression, and even modest reductions can be beneficial in NTG.³ Selective laser trabeculoplasty (SLT) has demonstrated efficacy and safety in lowering IOP in primary open-angle glaucoma and ocular hypertension, but its role in NTG is recently emerging and less clearly established. Recent studies suggest that SLT can achieve clinically meaningful IOP reductions and decrease IOP variability in NTG patients, potentially slowing disease progression.^{4,5} SLT may also be an effective and safe treatment option for NTG, as either a first-line or second-line treatment.⁶ Studies looking at long term outcomes found that SLT achieved a ~22% IOP reduction with a 41% decrease in medication use, but absolute success without medications declined from 61% at 6 months to 11% at 24 months, with many eyes requiring retreatment.⁷

Direct selective laser trabeculoplasty (DSLT) is an emerging variant of SLT that delivers laser energy without the need for a contact lens—making it a non-contact and potentially more patient-friendly procedure. However, in the GLAURious study that compares the efficacy of DSLT and SLT, NTG patients were excluded from the study and data on DSLT's effectiveness or safety specifically in NTG patients has not yet been reported in the peer-reviewed literature.⁸

Unmet Medical Need:

DSLT offers potential procedural advantages in open angle glaucoma and ocular hypertension but lacks evidence specific to NTG in current studies.

Study Objective

The objective of the study is to evaluate the safety and efficacy of direct selective laser trabeculoplasty (DSLT) in normal tension glaucoma (NTG) in Asian patient populations. Studies have indicated that NTG has higher prevalence in Asian populations.¹⁰

Study Hypothesis:

It is hypothesized that the use of DSLT leads to the reduction of medication and IOP in Asian NTG patients.

Study Design

The study is a 12-month prospective, single arm, single center interventional study evaluating the safety and efficacy of DSLT in NTG patients.

Study Cohort

The study cohort will consist of approximately 40 Asian eyes with NTG of all severities on 1-3 glaucoma medications.

Study Sample Size & Justification

The sample size determination is based on the requirement that data from 30 eyes will provide sufficient information to evaluate the clinical performance of the treatment in this single-arm study. To account for an anticipated rate of screen failures and subject discontinuations of 20-25%, the total planned enrollment is up to 40 eyes

Anticipated Study Duration

The study duration will be approximately thirty months

Study Endpoints

Primary Endpoint:

- 12 months absolute washed out IOP (and IOP reduction) compared to washed out IOP at baseline

Secondary Endpoints:

- # of medication reduction at 11 months
- Proportion of patients that are medication free at 11 months
- Proportion of patients achieving $\geq 10\%$, 15% , and 20% IOP reduction at 12 months
- Rate of secondary surgical intervention (SSI) at 12 months

Exploratory Endpoints:

- Visual field and nerve stability as defined by change in visual field mean deviation and optical coherence tomography of the retinal nerve fiber layer (OCT RNFL) thickness at 12 months compared to baseline

Study Methodology

- **Screening/Baseline Visit 1:** Patients with NTG (glaucomatous optic neuropathy in patients with IOP measurements consistently lower than 21 mmHg) on 1-3 glaucoma medications will be screened, enrolled, and receive informed consent. If patients qualify to take part in this study, they will undergo:
 - Completed dilated fundus exam (DFE), Humphrey visual field 24-2 test (HVF 24-2), optical coherence tomography of the retinal nerve fiber layer (OCT RNFL), and central corneal thickness (CCT) within inclusion range
 - Patients using glaucoma medications will undergo washout period of 6 weeks
 - Washed out IOP must be ≤ 21 mmHg, both eyes are eligible to enroll
 - Will restart patients back on meds (if any) for safety reasons (i.e. faster progression)
- **Visit 2:** Procedure Visit

- Patient will undergo DSLT (standard 1.8mJ, 120 shots, 360degrees)
- 1 drop tetracaine & brimonidine pre-procedure in treatment eye
- IOP check 5 mins and 1- 2 hours post-procedure
- As standard of care, IOP spikes and inflammation are treated at the discretion of the investigator
- One medication to be removed post-procedure
- Step down approach of medication removal for patient safety
- i.e. from 2 to 1 medication or 1 medication to no medication
- **Visit 3:** 1-month post-procedure (+/- 1 week)
 - IOP check
 - If IOP reduces $\geq 10\%$ from baseline screening medicated IOP then another medication is removed
 - Meds are reintroduced if IOP increases $>10\%$ from medicated baseline screening IOP
- **Visit 4 and 5:** 4 month and 8-month post- procedure (+/- 1 month)
 - As standard of practice, patients are seen every 3-4 months
 - IOP check
- **Visit 6:** 11 months- post-procedure (+/- 1month)
 - IOP check, not standard visit but prepare patient to do washout of medications (6 weeks)
- **Visit 7:** 12-13 months post-procedure
 - Washed-out IOP check
 - HVF 24-2, OCT, gonioscopy (check for PAS)
- Adverse event rates (IOP spike $>6\text{mmHg}$ and inflammation) and SSI will also be collected

Inclusion & Exclusion Criteria

Inclusion Criteria:

- Asian descent
- NTG diagnosis: glaucomatous optic neuropathy in patients with IOP measurements consistently lower than 21 mmHg
- Mean deviation (MD) of the visual field between 0 to -12dB
 - No significant central vision loss within 5 degrees within 5th percentile
- Age \geq 20 years
- NTG patients who are medically controlled on 1-3 medications and safe to wash out or IOP is still insufficient from medications and safe to washout
- Shaffer grade II or more on 3 of the 4 quadrants
- Central corneal thickness (CCT) 450–600 μ m
- All participants are able to provide written informed consent before participation

Exclusion Criteria:

- Angle closure glaucoma or narrow angle status post laser peripheral iridotomy (LPI), or any other open angle glaucoma excluding NTG
- History of SLT within last 2 years
- History intraocular surgery including refractive surgery, except for history of cataract surgery that has been greater than 1 year
- Patients anticipating cataract surgery during the study follow-up period
- Unable to have DSLT procedure due to pre-limbal findings
- Any presence of relevant ocular diseases including retinal disease with no confirmed cure

Study Visit Assessments

	Screening/ Baseline	Visit 2 Procedure	Visit 3 1M F/U	Visit 4&5 4&8 M F/U	Visit 6 11M F/U	Visit 7 12.5M F/U
Demographics		X				
Consent						

Medication	X	X	X	X	X	X
CCT	X					
Gonio	X					X
IOP	X (washed out)	X	X	X	X	X (washed out)
DSLT		X				

STUDY PRODUCT INFORMATION

See Appendix for DFU

Adverse Event Assessment

Adverse event assessments will be per Principal Investigator discretion

Statistical Analysis

Descriptive statistics will be prepared for all study timepoints. For continuous variables, summaries will include the sample size, mean, standard deviation, median, minimum, and maximum. For categorical variables, summaries will report the number and percentage of eyes in each category. Analyses will include all eyes that complete the study.

A planned sub-analysis will be conducted on the subset of patients with a prior history of selective laser trabeculoplasty (SLT) to assess whether treatment outcomes differed from those without prior SLT.

Study Milestones & Timelines

Milestones	Estimated Timelines
Contracting	November 2025
IRB Approval	December 2025
First Patient, First Visit (FPFV) date or Data Collection start date	February 2026
Last Patient, Last Visit (LPLV) date or Data Analysis start date	January 2028
Final Clinical Study Report (CSR)	March 2028

Procedures for Recording and Reporting

All AEs will be documented on the Adverse Event case report form (CRF) and collected on a routine basis at monitoring visits. Procedure-related postoperative conditions that are normal consequences of ocular procedure and not clinically relevant will only be reported as adverse events at the discretion of the Sponsor-Investigator.

In addition, the Sponsor-Investigator must document all SAEs with details including the date of occurrence, severity, treatment (if applicable), outcome, and assessments of the seriousness and causality. All available information must be submitted to the study monitor immediately (ie, within 24 hours of the Sponsor-Investigator's knowledge of the event).

The Sponsor-Investigator is responsible for reporting all adverse events, including product deficiencies, quality complaints, malfunctions, and events of special Interest to the investigational product's manufacturer, Alcon; irrespective of causality within 24 hours following first notification of the event. All subsequent follow-up information about the event should also be provided to Alcon. Sponsor-Investigator will send initial, and follow-up reports directly to the Alcon QA Medical Complaints team at **[contact]** using the appropriate forms.

The Sponsor-Investigator must also report all SAEs according to the requirements of regulatory authorities or IRB/IEC.

Follow-Up of Safety Information

The Sponsor-Investigator is responsible for adequate and safe medical care of subjects during the study and for ensuring that appropriate medical care and relevant follow-up procedures are maintained after the study. Any additional data from these follow-up procedures must be documented appropriately.

DATA REVIEW AND HANDLING

Completion of Study Records

All study data must be recorded directly on the approved study forms, which will serve as both the source documents and the case report forms for this Investigator-Initiated Trial (IIT). Data must be complete, accurate, and legible. Any discrepancies or missing information should be explained in the final report.

At a minimum, study records must include the following information for each subject:

- Subject identification (name, sex)
- Documentation of subject eligibility
- Date of informed consent and a copy of the signed consent form

- Dates of study visits
- Documentation that protocol-specific procedures were performed
- Results of study assessments, as required by the protocol
- Documentation of adverse events (AEs) and other safety parameters (as applicable)
- Records of medical history and use of concomitant therapies prior to and during the study
- Date of study completion and reason for early discontinuation (if applicable)

The Principal Investigator is responsible for reviewing and certifying the accuracy and completeness of the study records.

Subject identifiers must not be recorded beyond the subject number, demographic information, and/or other permitted study identifiers. Deviations from this protocol, regulatory requirements, and Good Clinical Practice (GCP) must be documented in the study records. An explanation for each deviation should be included, and any corrective and preventive actions must be documented by the Investigator.

ADMINISTRATIVE PROCEDURES

Regulatory and Ethical Compliance

This clinical study will be conducted in compliance with the protocol, current Good Clinical Practices, including the International Conference on Harmonization (ICH) Guidelines, and with the Declaration of Helsinki. In addition, all applicable local, state, and federal requirements relevant to the use of investigational products in the countries involved will be adhered to. The Sponsor-Investigator will ensure that all personnel involved in the conduct of the clinical study are qualified to perform their assigned duties through relevant education, training, and experience.

The Sponsor-Investigator assures that the key design elements of this protocol will be registered on www.clinicaltrials.gov as required by current regulations. In addition, the results of this study will be made publicly available on www.clinicaltrials.gov regardless of the outcome as required by current regulations as applicable.

Informed Consent Procedures

Voluntary informed consent will be obtained from every subject (and/or legal representative, as applicable) prior to the initiation of any screening or other clinical study-related procedures. The Sponsor-Investigator must have a defined process for obtaining consent. Specifically, the Sponsor-Investigator, or designee, will explain the clinical study to each potential subject, and the subject must indicate voluntary consent by signing and dating the approved informed consent form. The subject must be provided with an opportunity to ask questions of the Sponsor-Investigator, and if required by local regulation, other qualified personnel. The Sponsor-Investigator must provide the subject with a copy of the consent form written in a language the subject understands. The consent document must meet all applicable local laws

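### The 11-month medication count is biased toward a reduction: every eye loses a drug at Visit 2 whatever its IOP, and neither medication endpoint requires IOP to be held

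*Protocol*

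**What the plan says.** All references are to the protocol.

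- **Study Cohort**: every eye enters on 1 to 3 drugs. The **Inclusion Criteria** admit controlled eyes and also eyes whose "IOP is still insufficient from medications and safe to washout".
- **Study Methodology, Visit 2**: after the laser, "One medication to be removed post-procedure". No IOP or response criterion is attached. The example given is "i.e. from 2 to 1 medication or 1 medication to no medication".
- **Study Methodology, Visit 3 (1 month)**: if IOP is at least 10% lower, measured "from baseline screening medicated IOP then another medication is removed". In the other direction, "Meds are reintroduced if IOP increases" by more than 10% over the same reference.
- **Study Methodology, Visits 4 to 6**: IOP is checked, and Visit 6 also prepares the final washout. No rule for adding or removing drugs is written.
- **Secondary Endpoints**: the number "of medication reduction at 11 months" and the proportion medication free at the same time. Neither mentions IOP.
- **Study Hypothesis**: DSLT is expected to reduce both medication and IOP.
- **Study Design**: single arm.

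**The concern.** The protocol itself starts the fall in drug count. Every eye is one drug down on the day of the procedure, and a 1-drug eye is already medication free before any laser effect can be seen. The drug stays off unless one reading at 1 month exceeds the 10% limit. An eye whose IOP is 8% up at 1 month, or climbs further by month 11, still counts as reduced under the written rules.

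Reduced medication is half of the hypothesis. Without a control arm, nothing separates a reduced need for drugs from drugs that were simply stopped.

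The medication-free proportion has no single direction of bias. It is favoured in 1-drug eyes, harder to reach in 2-drug eyes (a second removal is needed), and has no written route in 3-drug eyes, because at most two removals are described.

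**Working it through.** The protocol gives no figure for the medication endpoints, so there is none to reproduce. The check asks what the written rules yield when the laser does nothing.

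**Inputs from the protocol.** One drug off at Visit 2; return if the 1-month change exceeds +10%; a second drug off if the change is −10% or lower and a drug remains.

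**Assumptions, not in the protocol.** Medicated IOP 13 mmHg; each removed drug adds 1 mmHg; SD of the change between two readings 2 mmHg; 1/2/3-drug mix 40/30/30; no change after Visit 3.

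**Closed form.** The threshold is 10% of 13 = 1.3 mmHg.

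- First drug stays off: Φ((1.3 − 1)/2) = Φ(0.15) = 0.56
- Second drug removed: Φ((−1.3 − 1)/2) = Φ(−1.15) = 0.125
- Mean drugs fewer: 0.56 + 0.6 × 0.125 = 0.635
- Medication free: 0.4 × 0.56 + 0.3 × 0.125 = 26%
- Medication free among 1- and 2-drug eyes only: 0.26/0.7 = 37%

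**Simulation.** SD 1.41 per reading, with each eye's 10% limit set on its own observed screening reading. That last feature makes results differ slightly from the closed form. Qualified means that Visit 6 IOP is also not more than 10% above medicated screening IOP. All rows are for an inert laser.

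| Rise per drug removed (mmHg) | 0.5 | 1 | 2 | 3 |
|---|---|---|---|---|
| *No change after Visit 3* | | | | |
| Drugs fewer | 0.75 | 0.62 | 0.39 | 0.22 |
| Any reduction, raw | 65% | 56% | 37% | 21% |
| Any reduction, qualified | 50% | 39% | 21% | 9% |
| Medication free, raw | 31% | 26% | 16% | 9% |
| Medication free, qualified | 24% | 18% | 9% | 4% |
| *One drug returned at Visits 4 and 5 if IOP >10% up* | | | | |
| Drugs fewer | 0.51 | 0.37 | 0.17 | 0.06 |
| Any reduction, raw | 43% | 33% | 16% | 6% |
| Any reduction, qualified | 37% | 27% | 12% | 4% |

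At a 1 mmHg rise with no later change, medication free by entry drug number (1, 2, 3) is 56%, 11% and 0% raw, and 40%, 8% and 0% qualified.

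**Range with no later change** (rise 0.5–3 mmHg; SD 1.5–2.5; mixes 40/30/30, 60/30/10 and 20/40/40): 0.14–0.80 drugs fewer, 14–69% reduced, 3–45% medication free.

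**Second model, on the percent scale.** Let removal raise IOP by r% and let the change have an SD of s% (8 to 15). The share still at least one drug down after Visit 3 is Φ((10 − r)/s): 75–89% at r = 0, 50% at r = 10, 11–25% at r = 20 and 3–16% at r = 25. It is positive in every case.

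**Does the qualified measure keep real responders?** With a laser that lowers IOP by 2 mmHg (rise 1, no later change), any reduction is 86% raw and 76% qualified. The gap from the inert laser goes from 86 − 56 ≈ 31 points (unrounded) to 76 − 39 = 37. For medication free (48% raw, 43% qualified) the gap goes from 22 to 24 points.

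**Cost in misclassification.** With no true change, one Visit 6 reading fails by chance with probability 1 − Φ(1.3/SD): 19%, 26% and 30% for SD 1.5, 2 and 2.5. Among eyes that passed Visit 3 it is 14%, 18% and 20%. SSI is not modelled.

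**The case against.** **Size.** The headline figures rest on assumed inputs. A 1-drug eye loses all its therapy, so its rise may well be larger. If removing the last drug adds 2 or 3 mmHg and the rest is unchanged, medication free in 1-drug eyes falls from 56% to 36% or 20%, and overall from 26% to 18% or 12%. This stands: the size is not fixed.

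**Re-treatment.** Visits 4 and 5 follow ordinary practice, and under Follow-Up of Safety Information "The Sponsor-Investigator is responsible for adequate and safe medical care of subjects during the study". Nothing bars returning a drug later, and the Visit 3 return rule could be read as a continuing principle, although its placement argues otherwise. With returns and a 3 mmHg rise, only 0.06 drugs and 6% of eyes remain. This also stands as a limit on size. It leaves the count dependent on unwritten judgement in an open study, and the expected reduction stays above zero.

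**Other evidence.** The pre-laser washout shows what drug removal does without the laser, and the washed-out primary endpoint tests the laser directly. Both are true, but neither medication endpoint uses that comparison.

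**Weight.** The endpoints are secondary and descriptive, with about 30 evaluable eyes. That limits the severity. It does not make the count a fair reading of half of the hypothesis.

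**Partial remedy.** An inert laser still shows 39% qualified against 56% raw, so about 70% of the artefact survives. Conceded: the remedy reduces the bias and does not remove it.

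**Conclusion.** The concern holds. Followed exactly, the written rules produce a positive expected drug reduction under an inert laser in every scenario tried. The direction follows from the text: removal is unconditional, the single written return rule rests on one 1-month reading, and neither endpoint has an IOP condition. The size rests on assumptions. It is about 0.63 drugs and 56% of eyes in the middle case with no later change, 0.37 drugs and 33% with returns at Visits 4 and 5, and small where the removed drug was working well. The medication-free proportion is distorted in a way that depends on the entry drug mix. The primary endpoint is untouched. This should be corrected, but it does not threaten the main result.

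**What to change.** 1. Beside the raw counts, report the proportion with reduced medication and the proportion medication free, counting only eyes whose Visit 6 IOP is not more than 10% above medicated screening IOP and that had no SSI. Show each by entry drug number (1, 2, 3).
2. State that the uncontrolled drug count does not by itself support the medication part of the hypothesis.
3. Write the medication rule for Visits 4 to 6, including a step for 3-drug eyes. A written return rule would also shrink the artefact: in the middle case, returns at Visits 4 and 5 take 0.62 drugs down to 0.37.
4. Do not restrict the medication-free endpoint to 1- and 2-drug eyes; that raises the inert-laser rate from 26% to 37%.

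The cost is protocol wording and one table. Visit 6 drug count and IOP are already collected, and the Visit 3 rule already needs the medicated screening IOP. Reported rates will look lower. A single Visit 6 reading will fail some truly unchanged eyes (14–20% of those that kept the reduction at Visit 3). Strata will be small: about 12, 9 and 9 of 30 eyes under a 40/30/30 mix. For eyes that entered with insufficient IOP, the 10% band remains lenient.

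### A late but in-window Visit 6 leaves too little time for the stated 6-week washout before the Visit 7 window closes

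*Protocol*

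**What the plan says.** All the timing rules are in the Protocol.

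- **Visit 6** (Study Methodology) is at "11 months- post-procedure (+/- 1month"), that is, months 10 to 12. Its purpose is given as "IOP check, not standard visit but prepare patient to do washout of medications (6 weeks").
- **Visit 7** (Study Methodology) is at "12-13 months post-procedure", with no further tolerance, and its IOP is to be taken washed out. The Study Visit Assessments table labels the visit 12.5 months.
- **Primary endpoint** (Study Endpoints): "12 months absolute washed out IOP (and IOP reduction) compared to washed out IOP at baseline".
- **Baseline** (Study Methodology, Screening/Baseline Visit 1): "Patients using glaucoma medications will undergo washout period of 6 weeks".
- **Analysis set** (Statistical Analysis): "Analyses will include all eyes that complete the study".
- **Records** (Data Review and Handling): sites keep visit dates and "Records of medical history and use of concomitant therapies prior to and during the study". In addition, "Deviations from this protocol, regulatory requirements, and Good Clinical Practice (GCP) must be documented in the study records".

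No section ranks the washout length against the Visit 7 window.

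**The concern.** The Visit 6 tolerance, the 6-week washout and the Visit 7 window each look reasonable alone. Together they cannot all be met for an eye still on medication whose Visit 6 falls late in its permitted range. The site then has two choices:

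- **(a) Keep the Visit 7 window.** IOP is read after a washout shorter than the one used at baseline. Any residual drug effect would lower IOP, and with no control arm it would be credited to the laser. The same reading feeds the secondary endpoints on 10%, 15% and 20% IOP reduction.
- **(b) Keep the washout.** The comparison with baseline stays like for like on washout, but the 12-month reading is taken after month 13, outside the Protocol's own window.

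Different eyes could follow different branches and then be pooled, because the analysis takes every completing eye.

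Eyes still on drops at Visit 6 are foreseeable. Patients enter on 1 to 3 medications, and the stated steps remove one after the procedure and, if IOP has fallen enough, one more at month 1. On those steps alone, an eye entering on three still has 3 − 2 = 1 at Visit 6. Medications may also be reintroduced.

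**Working it through.** **Inputs.** Visit 6 window: months 10 to 12. Washout: 6 weeks = 42 days. Visit 7 window: months 12 to 13. Nominal times: 11 and 12.5 months. Month length: 365.25/12 = 30.4375 days, varied below.

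**Assumption.** Washout starts on the day of Visit 6. The text says only that the patient is prepared then, and a later start moves the cut-off earlier. A start before Visit 6 fits poorly, since medication count and medication-free status are endpoints at 11 months.

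**1. The nominal schedule.** 42 / 30.4375 = 1.380 months, and 11 + 1.38 = month 12.38, consistent with the table's 12.5. From month 11.0 to 12.5 is 1.5 × 30.4375 = 45.7 days, a slack of 45.7 − 42 = 3.7 days. It works.

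**2. Latest workable Visit 6.** 13 − 1.380 = month 11.620.

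**3. Share of the window in conflict.** (12 − 11.620) / 2 = 19.0% of the dates, or 0.380 × 30.4375 = 11.6 days.

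**4. Size of the conflict for a given Visit 6.** Longest in-window interval = (13 − Visit 6) × 30.4375. Shortfall = 42 − that interval. The overrun past month 13 after a full washout is the same number of days.

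| Visit 6 (month) | Longest interval to month 13 (days) | Smallest shortfall, branch (a), or overrun, branch (b) (days) |
|---|---|---|
| 11.62 | 42.0 | 0 |
| 11.8 | 36.5 | 5.5 |
| 12.0 | 30.4 | 11.6 |

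From month 12.0, a full washout ends at 12 + 1.380 = month 13.38. Under branch (a), an earlier in-window Visit 7 would shorten the washout further.

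**5. Sensitivity to month length.**

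| Days per month | Cut-off (month) | Share of Visit 6 window | Days |
|---|---|---|---|
| 28 | 11.50 | 25.0% | 14 |
| 30 | 11.60 | 20.0% | 12 |
| 30.4375 | 11.62 | 19.0% | 11.6 |
| 31 | 11.645 | 17.7% | 11 |

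With real calendar dates, for procedures on each day of a year from March 2026, 11 to 13 days are affected.

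**6. The early side.** There is no conflict. A Visit 6 before 12 − 1.380 = month 10.62 only means that washout starts later or runs longer.

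**7. Weight of one eye.** With about 30 completing eyes, one eye moves a responder rate by 1/30 = 3.3 percentage points. Both eyes of a patient may enrol, so one late visit can affect two.

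**The case against.** The strongest reply is that the windows permit the conflict but do not force it. About 81% of Visit 6 dates, the nominal one included, leave room for the full washout, and a single centre booking a visit whose purpose is to prepare that washout can see the constraint. The text also leans towards the washout: washed-out status is named in the primary endpoint, in the Visit 7 description and in the assessments table, and 6 weeks is the only length given. On that reading the cost is a Visit 7 at most about 12 days late. The documents give no drug class or washout kinetics, so the bias in branch (a) is not demonstrated. Medication is recorded at Visits 6 and 7, and deviations must be documented and explained, so a short washout should be visible. A sensitivity analysis could sit in the SAP.

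Much of this stands, and it limits the weight of the point: few eyes, possibly none, may be affected, and no bias can be sized. The 12.5-month label lies inside the Visit 7 window and is not itself an error. What does not stand is that these points remove the conflict. The triggering Visit 6 is in window, so it is not a deviation, and recording the consequence does not tell the site which rule to follow. A lean in the wording is not a precedence rule, and no later analysis can restore a washout that was not completed.

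**Conclusion.** The concern holds. For an eye still on drops, a Visit 6 after about month 11.62 (11.50 to 11.65 across month conventions) complies with the Protocol but has no compliant Visit 7. The unavoidable washout shortfall, or the overrun past month 13, rises from 0 to 11.6 days at month 12.0. This rests on washout starting on the day of Visit 6 and on reading the Visit 7 window as having no further tolerance.

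Visit 6 dates up to month 11.62 and medication-free eyes are unaffected. Neither the number of affected eyes nor the size or presence of residual drug effect can be derived from the Protocol. It should be corrected because it bears on the primary reading in an uncontrolled study and can be prevented only beforehand, but it does not threaten the design as a whole.

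**What to change.** Reconcile the Visit 6 window, the Visit 7 window and the 12-month endpoint label with the Protocol's own washout, so that every permitted Visit 6 date leaves the stated interval before an in-window Visit 7. Timing Visit 7 from the recorded start of washout is one way. Which window changes is for the sponsor to decide, and no washout length or clinical rule is proposed here. Check that the assessments table's label for Visit 7 still agrees afterwards.

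Record the last-drop date for each eye. Report the primary result also without eyes whose washout was shorter than stated; this can be placed in the SAP.

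The cost is a minor amendment to the visit text and one date field, since visit dates and concomitant therapies are already required records. Some visit dates will shift, and the sensitivity set may be slightly smaller than the roughly 30 completing eyes.

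### The restart rule can sit above an eye's untreated IOP, so a DSLT with no effect can be counted as medication reduction at month 11

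*Protocol*

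**What the plan says.** All of this is in the Protocol.

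- **Inclusion Criteria.** Both controlled and under-controlled eyes qualify: "NTG patients who are medically controlled on 1-3 medications and safe to wash out or IOP is still insufficient from medications and safe to washout". The pressure limit after washout is an upper one only: "Washed out IOP must be ≤ 21 mmHg". No minimum difference between medicated and washed-out IOP is required.
- **Study Methodology, Screening/Baseline.** After washout: "Will restart patients back on meds (if any) for safety reasons (i.e. faster progression").
- **Visit 2.** "One medication to be removed post-procedure", with no exception. A one-drug eye goes to none. The stated reason is "Step down approach of medication removal for patient safety".
- **Visit 3.** Further removal: "If IOP reduces $\geq 10\%$ from baseline screening medicated IOP then another medication is removed". Restart: "Meds are reintroduced if IOP increases $>10\%$ from medicated baseline screening IOP".
- **Visits 4 and 5.** An IOP check, with no drug rule.
- **Visit 6 (month 11).** "IOP check, not standard visit but prepare patient to do washout of medications (6 weeks").
- **Secondary Endpoints.** The number of drugs removed and the proportion free of drugs, both at month 11 and neither tied to IOP.
- **Study Design and Study Hypothesis.** Single arm. Reduction of both medication and IOP is attributed to DSLT.

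**The concern.** The first drug is removed by rule, not in response to the laser. A later drug count says something about DSLT only if the restart rule puts the drug back in eyes where DSLT did not replace it. That rule is tied to medicated IOP, so the weaker the drops, the closer the threshold comes to untreated IOP, until it passes it. Beyond that point no IOP rise from stopping the drops can trigger a restart, apart from reading error. With no control arm, nothing in the drug endpoints separates that outcome from a laser effect.

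There is a second, smaller matter. For eyes enrolled with IOP still insufficient, the rule accepts up to 10% above a pressure the protocol has already called inadequate. That fits poorly with its own reasons for stepping down gradually and for restarting drops after washout.

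**Working it through.** **Inputs from the Protocol.** Restart above 1.10 × medicated screening IOP (Visit 3); one drug removed from every eye (Visit 2); 30 eyes expected to complete (30 / (1 − 0.25) = 40, the planned enrolment). The Protocol gives no figure of its own for the restart rule to reproduce.

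**Assumptions.** Untreated IOP 18 mmHg; drop effects of 5% to 20%; independent normal reading error with SD 1.5 mmHg (range 1.0 to 2.0); no discretionary restart.

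**1. Break-even.** Let W be untreated IOP and e the fraction by which the drops lower it, so medicated IOP is M = W(1 − e). The threshold exceeds untreated IOP when 1.10 × W(1 − e) > W, that is e < 1 − 1/1.10 = 9.1%. W cancels, and the eye's class (controlled or insufficient) does not enter.

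**2. One-drug eye, W = 18, zero DSLT effect.** IOP returns to 18.0.

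| Drop effect | M | Restart above | Restarted at 18.0? |
|---|---|---|---|
| 5% | 17.10 | 18.81 | No |
| 8% | 16.56 | 18.22 | No |
| 15% | 15.30 | 16.83 | Yes |
| 20% | 14.40 | 15.84 | Yes |

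**3. With reading error.** Both the Visit 3 reading and the medicated reading vary, so P(no restart) = Φ((1.1M − W) / (SD × √(1 + 1.21))). At SD 1.5 (range for SD 1.0 to 2.0):

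- 5% drop effect: 64% (61–71%)
- 8%: 54% (53–56%)
- 15%: 30% (22–35%)
- 20%: 17% (7–23%)

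The last two come from reading error alone.

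**4. Two-drug eye.** The 9.1% limit then applies to what the removed drug adds. Take W = 16, a first drug worth 20% and a removed drug worth a further 5%. M = 16 × 0.80 × 0.95 = 12.16, IOP after removal is 12.80, and restart comes only above 1.1 × 12.16 = 13.38. An inert DSLT is counted as one drug fewer.

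**5. Second removal.** An inert DSLT meets the further-removal rule at Visit 3 only through reading error. The problem lies in the unconditional first removal combined with the restart rule.

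**6. Weight per eye.** 1/30 = 3.3 percentage points of the medication-free proportion, if 30 eyes are the denominator.

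**7. Check of the fix.** Simulation of 2,000,000 one-drug eyes, W = 18, e = 8%, with independent errors on the medicated, washed-out and Visit 3 to 6 readings. Change (a) restarts at Visits 3, 4 or 5 if the reading exceeds the lower of 1.1 × the medicated reading and the washed-out reading. Change (b) counts the eye only if its month-11 reading is at or below the medicated reading. Counted medication free at SD 1.5 (range for SD 1.0 to 2.0):

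| True DSLT effect | Present rules | (a) + (b) |
|---|---|---|
| 0 | 54% (53–56%) | 5% (3–6%) |
| 20% | 96% (90–99%) | 72% (55–92%) |

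**The case against.** The strongest reply has five parts.

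- **The insufficient limb is not the cause.** A reader might infer that admitting insufficient eyes creates the fault. It does not. A controlled eye with a 5% drop response has the same threshold problem, and an insufficient eye with a 20% response does not. This stands. For insufficient eyes, what remains is the tolerance of 10% above an inadequate pressure.
- **The hypothesis is not confirmed by an inert laser.** A reader might infer that DSLT could succeed on the study's hypothesis with no effect. The hypothesis joins medication and IOP. The primary endpoint is washed out at both ends, and the responder endpoints use the month-12 IOP, also taken after washout. These would show the lack of effect. This stands: the damage is confined to two secondary endpoints, reported descriptively.
- **Eyes are not left without care.** A reader might infer that under-treated eyes are abandoned. The criterion requires that washout be safe, IOP and medication are recorded through follow-up, and the investigator is responsible for safe care. In the weak-response case the drug given up was worth less than 9.1%, about 1.6 mmHg at 18. This stands as to safety. But a discretionary restart means unmasked judgement, not the stated rule, sets the drug endpoint.
- **The share is unknown, and reading error affects any single-reading rule.** Both are true. The 30% and 17% figures are not evidence against this anchor. The break-even at 9.1% does not depend on reading error.
- **Unconditional first removal belongs to a step-down design, and the analysis plan could add an IOP condition.** The first part is accepted, and Visit 2 need not change. On the second, the restart rule is treatment conduct fixed in the protocol, and an analysis plan cannot put a drug back.

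**Conclusion.** The point holds as a matter of what the stated rules do when followed exactly. In any eye whose drops lower IOP by less than 9.1%, the restart threshold lies above untreated IOP. A one-drug eye of this kind can be counted medication free after a DSLT that did nothing. With more drugs, the same applies to the removed drug's own contribution, and the eye counts as one drug fewer.

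The break-even rests on the protocol alone. The percentages rest on an assumed untreated IOP, drop effect and reading error. How many eyes are affected cannot be derived from the document, so no overall bias in the endpoint can be stated. The primary and responder endpoints are sound on this point. The change is worth making because it is cheap and because, without a control arm, the drug endpoints have no other safeguard.

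**What to change.** Two changes. Neither needs a target IOP for each eye or a change to the Visit 2 removal.

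- **(a) Restart rule.** Apply it at Visits 3, 4 and 5. Restart when IOP is more than 10% above medicated screening IOP or has reached the eye's washed-out baseline IOP, whichever threshold is lower.
- **(b) Month-11 drug endpoints.** Count a drug reduction, or an eye as medication free, only if its month-11 IOP is at or below medicated screening IOP. Report the unconditional count beside it.

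In the two-drug example only (b) acts: 12.80 is below both restart thresholds but above the medicated 12.16, so the eye is not counted.

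**Cost.** New text for Visits 3 to 5 and the two endpoints, and no extra visits: IOP is already checked at months 4, 8 and 11, and the Visit 3 rule already needs the medicated screening value. Some drops are restarted earlier. Fewer eyes count as drug successes, 72% rather than 96% in the example with a true 20% effect. Part of that loss is reading error, since an eye must now pass several single readings; the unconditional count shows how much the condition at month 11 removes. The primary endpoint and the number of eyes do not change.
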